## **7.0 TRIAL PROCEDURES**

### **7.1 Trial Procedures**

The Trial Flow Chart - Section 6.0 summarizes the trial procedures to be performed at each visit. Individual trial procedures are described in detail below. It may be necessary to perform these procedures at unscheduled time points if deemed clinically necessary by the investigator.

Furthermore, additional evaluations/testing may be deemed necessary by the investigator and or the Sponsor for reasons related to subject safety. In some cases, such evaluation/testing may be potentially sensitive in nature (e.g., HIV, Hepatitis C, etc.), and thus local regulations may require that additional informed consent be obtained from the subject. In these cases, such evaluations/testing will be performed in accordance with those regulations.

#### **7.1.1 Administrative Procedures**

##### **7.1.1.1 Informed Consent**

The investigator or qualified designee must obtain documented consent from each potential subject or each subject's legally acceptable representative prior to participating in a clinical trial or Future Biomedical Research. If there are changes to the subject's status during the trial (e.g., health or age of majority requirements), the investigator or qualified designee must ensure the appropriate consent is in place.

###### **7.1.1.1.1 General Informed Consent**

Consent must be documented by the subject's dated signature or by the subject's legally acceptable representative's dated signature on a consent form along with the dated signature of the person conducting the consent discussion.

A copy of the signed and dated consent form should be given to the subject before participation in the trial.

The initial informed consent form, any subsequent revised written informed consent form and any written information provided to the subject must receive the IRB/ERC's approval/favorable opinion in advance of use. The subject or his/her legally acceptable representative should be informed in a timely manner if new information becomes available that may be relevant to the subject's willingness to continue participation in the trial. The communication of this information will be provided and documented via a revised consent form or addendum to the original consent form that captures the subject's dated signature or by the subject's legally acceptable representative's dated signature.

Specifics about a trial and the trial population will be added to the consent form template at the protocol level.

The informed consent will adhere to IRB/ERC requirements, applicable laws and regulations and Sponsor requirements.

#### 7.1.1.1.2 Consent and Collection of Specimens for Future Biomedical Research

The investigator or qualified designee will explain the Future Biomedical Research consent to the subject, answer all of his/her questions, and obtain written informed consent before performing any procedure related to the Future Biomedical Research sub-trial. A copy of the informed consent will be given to the subject.

#### 7.1.1.2 Inclusion/Exclusion Criteria

All inclusion and exclusion criteria will be reviewed by the investigator or qualified designee to ensure that the subject qualifies for the trial.

#### 7.1.1.3 Subject Identification Card

All subjects will be given a Subject Identification Card identifying them as participants in a research trial. The card will contain trial site contact information (including direct telephone numbers) to be utilized in the event of an emergency. The investigator or qualified designee will provide the subject with a Subject Identification Card immediately after the subject provides written informed consent. At the time of treatment allocation/randomization, site personnel will add the treatment/randomization number to the Subject Identification Card.

The subject identification card also contains contact information for the emergency unblinding call center so that a health care provider can obtain information about trial medication/vaccination in emergency situations where the investigator is not available.

#### 7.1.1.4 Medical History

A medical history will be obtained by the investigator or qualified designee. A detailed medical history must be documented, including:

- non-cancer medical history
- concurrent illnesses
- demographics
- diagnosis and prior treatments for malignancies

#### 7.1.1.5 Prior and Concomitant Medications Review

##### 7.1.1.5.1 Prior Medications

The investigator or qualified designee will review prior medication use, including any protocol-specified washout requirement, and record prior medication taken by the subject within 4 weeks or 5 half-lives before first dose of trial medication.

##### 7.1.1.5.2 Concomitant Medications

The investigator or qualified designee will record medication, if any, taken by the subject during the trial.

#### 7.1.1.6 Assignment of Screening Number

All consented subjects will be given a unique screening number that will be used to identify the subject for all procedures that occur prior to randomization or treatment allocation. Each subject will be assigned only one screening number. Screening numbers must not be re-used for different subjects.

Any subject who is screened multiple times will retain the original screening number assigned at the initial screening visit.

Specific details on the screening visit requirements (screening/rescreening) are provided in Section 7.1.5.1.

#### 7.1.1.7 Assignment of Treatment/Randomization Number

All eligible subjects will be allocated, by non-random assignment, and will receive a treatment/randomization number. The treatment/randomization number identifies the subject for all procedures occurring after treatment allocation/randomization. The assigned screening number will become the subjects' treatment allocation number. Once a treatment/randomization number is assigned to a subject, it can never be re-assigned to another subject.

A single subject cannot be assigned more than 1 treatment/randomization number.

#### 7.1.1.8 Trial Compliance

Administration of the investigational product will be supervised by the investigator. Any delegation of this responsibility must be documented.

In practice, on study visit days study nurses will supervise the intake of the appropriate MK-8628 dose, explaining to subjects the exact number of capsules they should take. Nurses will document in the eCRF the administration, the dose, the time of administration, as well as any immediate reactions at the time of intake.

For non-visit days, MK-8628 will be taken at home. Subjects will record daily in a specific diary, the number of capsules swallowed, time of intake, as well as possible reactions, including vomiting, and their date/time of occurrence.

When a subject attends a study visit, he/she will bring any unused capsules and their diary. According to the center procedures, the diary will be used to complete the eCRF treatment administration section, either directly as a Source Document or as an aid for completing the nurse's notes which will be used as a Source Document.

Interruptions from the protocol specified treatment > 2 weeks require consultation between the investigator and the Sponsor and written documentation of the collaborative decision on subject management.

## **7.1.2 Clinical Procedures/Assessments**

### **7.1.2.1 Adverse Event (AE) Monitoring**

The investigator or qualified designee will assess each subject to evaluate for potential new or worsening AEs as specified in the Trial Flow Chart and more frequently if clinically indicated. Adverse experiences will be graded and recorded throughout the study and during the follow-up period according to NCI CTCAE Version 4.0. Toxicities will be characterized in terms including seriousness, causality, toxicity grading and action taken with regard to trial treatment.

Please refer to Section 7.2 for detailed information regarding the assessment and recording of AEs.

### **7.1.2.2 Full Physical Exam**

The investigator or qualified designee will perform a complete physical exam during the screening period. Clinically significant findings should be recorded as medical history. After the first dose of trial treatment, new clinically significant abnormal findings should be recorded as AEs. A final full physical exam should be completed during the end of treatment visit.

### **7.1.2.3 Directed Physical Exam**

For cycles that do not require a full physical exam per the Trial Flow Chart, the investigator or qualified designee will perform a directed physical exam as clinically indicated prior to trial treatment administration. New clinically significant abnormal findings should be recorded as AEs.

### **7.1.2.4 Eastern Cooperative Oncology Group (ECOG) Performance Scale**

The investigator or designee will assess the ECOG status (see Section) at screening, prior to trial administration on Day 1 of each cycle, and during the post-treatment follow-up period.

### **7.1.2.5 Vital Signs**

The investigator or qualified designee will take vital signs at screening, prior to trial administration on day 1 of each cycle, and during the treatment discontinuation visit as specified in the Trial Flow Chart. Vital signs include heart rate, blood pressure, body temperature, and weight.

### **7.1.2.6 12 Lead Electrocardiogram (ECG)**

The investigator or qualified designee will take 12 lead ECGs as specified in the Trial Flow Chart. ECGs collected on cycle 1 day 1 should be taken at the following time points:

- Pre-dose
- 1 hour post-dose
- 2 hours post-dose

After cycle 1, ECGs should be collected on day 1 of every odd cycle (every 6 weeks) at the pre-dose (prior to dosing) time point.

#### 7.1.2.7 Tumor Assessment / Response Evaluation

Tumor response should be assessed on the cycle days depicted in section 6.0, and based on the criteria displayed in Sections 7.1.2.7.1 and 7.1.2.7.2.

##### 7.1.2.7.1 Bone Marrow Aspiration / Biopsy & Criteria for Response Assessment - AML

The anti-tumor activity of MK-8628 will be evaluated as part of the efficacy endpoints using the following criteria:

- Diagnosis and management of acute myeloid leukemia in adults: recommendations from an international expert panel, on behalf of the European LeukemiaNet (Döhner et al, *Blood*, 2010)] See Appendices 12.4.

These International Working Group criteria will be applied by the site as the primary measure for assessment of disease response and as a basis for all protocol guidelines related to disease status (e.g. discontinuation of study therapy). The assessments will be completed through analysis of bone marrow aspiration samples, and bone marrow biopsy samples (if necessary). The timing for tumor response assessments should follow calendar days and should not be adjusted for delays in cycle starts.

Tumor assessment and response evaluation should be completed at the following visits:

- Screening
- Cycle 2 day 1 ( $\pm$  3 days)
- Cycle 3 day 1 ( $\pm$  3 days)
- \*Beyond Cycle 3
- Treatment Discontinuation Visit

\*\*Follow-up Visits (every 6 weeks post-treatment,  $\pm$  3 days)\*Response assessments will be conducted on day 1 of every cycle ( $\pm$  3 days) beyond cycle 3 through hematological analysis of peripheral blood. Evidence of response or progression in peripheral blood may be confirmed by further bone marrow assessments as displayed in Section 12.4.

\*\*In subjects who discontinue study therapy without documented disease progression, every effort should be made to continue monitoring their disease status every 6 weeks ( $\pm$  3 days) until (1) the start of new anti-cancer treatment, (2) documented disease progression, (3) death, or (4) the end of the study, whichever occurs first. If subjects have stable disease, partial response, or complete response, they should continue on this assessment schedule. Tumor response assessments should occur at any time where there is clinical suspicion of progression.

#### 7.1.2.7.2 Positron Emission Tomography (PET), Computed Tomography (CT), & Criteria for Response Assessment - DLBCL

The anti-tumor activity of MK-8628 will be evaluated as part of the efficacy endpoints using the following International Working Group criteria:

- 5 Point-Scale per the Lugano Classification (Cheson et al, *J Clin Oncol*, 2014) [46]  
See Appendices 12.5.

These International Working Group criteria will be applied by the site as the primary measure for assessment of disease response and as a basis for all protocol guidelines related to disease status (e.g. discontinuation of study therapy). The assessments will involve the use of PET-CT and CT imaging (PET based response to analyze FDG-avid uptake using a 5 point scale, and confirm residual vs. metabolically active tumor locations). The timing of tumor response assessments should follow calendar days and should not be adjusted for delays in cycle starts. The same imaging technique should be used in a subject throughout the trial. Local reading (investigator assessment with site radiology reading) will be used to determine eligibility and for subject management. The sponsor may potentially collect radiologic assessments for retrospective analysis by a central vendor. Assessment of lymphoma B symptoms should occur with each lymphoma disease response assessment.

The tumor response assessments should be completed at the following visits:

- \*Screening
- Cycle 5 day 1 (Week 12,  $\pm$  3 days) and every 12 weeks thereafter ( $\pm$  3 days)
- \*\* Treatment Discontinuation Visit
- \*\*\*Follow-up Visits (every 12 weeks post-treatment,  $\pm$  7 days)

\*Routine imaging (or bone marrow biopsy) performed outside of the scope of this study will be acceptable to complete the criteria for response assessment at screening, if performed  $\leq$  4 weeks prior to study entry.

\*\*In subjects with an unconfirmed PD assessment, a radiological assessment should be performed at the time of treatment discontinuation. If previous scan was obtained within 4 weeks prior to the date of discontinuation, then a repeat scan at treatment discontinuation isn't mandatory. However, imaging should occur at any time where there is clinical suspicion of progression.

\*\*\*In subjects who discontinue study therapy without documented disease progression, every effort should be made to continue monitoring their disease status every 12 weeks ( $\pm$  7 days) until (1) the start of new anti-cancer treatment, (2) documented disease progression, (3) death, or (4) the end of the study, whichever occurs first. If subjects have stable disease, partial response, or complete response, they should continue on this assessment schedule. Tumor response assessments should occur at any time where there is clinical suspicion of progression.

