Estimated duration of trial	The Sponsor estimates that the trial will require approximately 20 months from the time the first subject signs the informed consent until the last subject's last study-related phone call or visit.

Duration of Participation	Each subject will participate in the trial from the time the subject signs the Informed Consent Form (ICF) through the final contact. After a screening phase of up to 2 weeks, eligible subjects will receive treatment according to their assigned regimen and dose level in 3-week dosing cycles. Treatment with MK-8628 will continue until documented disease progression, unacceptable toxicity, subject withdrawal of consent, subject non-compliance with trial treatment or procedure requirements, treatment interruption > 2 weeks for any reason (except in the event of perceived benefit, with Sponsor agreement), recurrence of dose limiting toxicity (DLT) despite dose reduction (except in the event of perceived benefit, with Sponsor agreement), or by the investigators decision to withdraw the subject. After the end of treatment, subjects are to be followed up for safety for at least 30 days following the last MK-8628 dosing and until recovery or stabilization of all related toxicities.
---------------------------	--

A list of abbreviations used in this document can be found in Section 12.9.

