#### 5.1.2 Subject Inclusion Criteria

In order to be eligible for participation in this trial, the subject must:

1. Be willing and able to provide written informed consent for the trial. Study entry is defined as the date that subject provides written informed consent. The subject may also provide consent for Future Biomedical Research. However, the subject may participate in the main trial without participating in Future Biomedical research.
2. Be  $\geq 18$  years of age on the day of providing written informed consent.
3. Have an ECOG performance status score of  $\leq 1$ .
4. Have an interval of  $\geq 3$  weeks since chemotherapy ( $\geq 6$  weeks for nitrosoureas or mitomycin C), immunotherapy, hormone therapy or any other anticancer therapy (including investigational) or surgical intervention resection, or  $\geq 3$  half-lives for monoclonal antibodies, or  $\geq 5$  half-lives for other non-cytotoxic agents (whichever is longer).
5. Female subjects of childbearing potential must have a negative urine or serum pregnancy test within 72 hours prior to receiving the first dose of study medication. If the urine test is positive or cannot be confirmed as negative, a serum pregnancy test will be required.
6. Female subjects of childbearing potential should be willing to use an adequate method of contraception as outlined in section 5.7.3 - Contraception, for the course of the study through 90 days after the last dose of study medication. Note: Abstinence is acceptable if this is the usual lifestyle and preferred contraception for the subject.
7. Male subjects of childbearing potential 5.7.3 – Contraception, starting with the first dose of trial treatment through 90 days after the last dose of study medication. Note: Abstinence is acceptable if this is the usual lifestyle and preferred contraception for the subject
8. Demonstrate adequate organ function as defined in [Table 1](#) below. All screening labs should be performed within 7 days of treatment initiation.

Table 1 Adequate Organ Function Laboratory Values

System	Laboratory Value
Hematological	
Absolute neutrophil count (ANC)	AML Subjects = No Limit DLBCL Subjects = $\geq 1.0 \times 10^9/L$
Platelets	AML Subjects = No Limit DLBCL Subjects = $\geq 150 \times 10^9/L$ (4 weeks without transfusion)
Hemoglobin	AML Subjects = No Limit DLBCL Subjects = $\geq 8.0 \text{ g/dL}$ (4 weeks without transfusion)
Renal	

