#### Allowed

Listed below are allowed concomitant medications / therapy during the course of the trial:

1. Supportive treatment of symptoms/adverse events or standard treatment of concomitant conditions, notably transfusion support and antibiotics or bisphosphonates will be given as medically indicated and reported in the eCRF.
2. Chemotherapy, hormone therapy or any other anticancer therapy or surgical intervention resection performed  $\geq$  3 weeks prior to study start ( $\geq$  6 weeks for nitrosoureas or mitomycin C) or  $\geq$  3 half-lives for monoclonal antibodies or  $\geq$  5 half-lives for other non-cytotoxic agents (whichever is longer).
3. Subjects on anticoagulant or antiaggregant (including low-dose aspirin) therapy at screening for concomitant medical conditions should be evaluated in coordination with their cardiologist for the benefit/risk ratio of continuing their anticoagulant or antiaggregant therapy during the study due to the potential increased risk of bleeding in the event of occurrence of severe thrombocytopenia. Blood cell count should be performed more frequently in such subjects, at least weekly throughout study, and more often in cases of grade 2 to 3 thrombocytopenia.

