#### 7.1.5.1 Screening

Each candidate subject will be examined before starting the study to determine eligibility for participation as set forth in Section 5.1. This must be done within 2 weeks prior to the first study treatment administration (exceptions listed below). Screening procedures may be repeated after consultation with the Sponsor.

Written consent must be obtained prior to performing any protocol specific procedure. Results of a test performed prior to the subject signing consent as part of routine clinical management are acceptable in lieu of a screening test if performed within the specified time frame.

Screening procedures are to be performed within 2 weeks prior to the first dose of trial treatment except for the following:

- For women of reproductive potential, a urine or serum pregnancy test will be performed within 72 hours prior to the subject's first dose of trial treatment on cycle 1 / day 1.

- The following assessments need to be completed within a 7 day window (day -7 to day -1) prior to the subject's first dose of trial treatment on cycle 1 / day 1:
  - Complete Blood Count (CBC)
  - PT-International Normalized Ratio (INR), aPTT, and Factor VII
  - Serum Chemistry
- The following is applicable to DLBCL subjects only: routine imaging (or bone marrow biopsy) performed outside of the scope of this study will be acceptable to complete the Response Criteria for Malignant Lymphoma (Section 7.1.2.7.2) at screening, if performed  $\leq$  4 weeks prior to study entry.

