## 8.3 Hypotheses/Estimation

Objectives of the study are stated in Section 3.0.

There are no statistical hypotheses for this study.

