## 8.9 Sample Size and Power Calculations

The study is designed to assess the safety of MK-8628 in subjects with selected hematologic malignancies. The small numbers per cohort are not intended for statistical hypotheses.

Up to 28 evaluable subjects will be included in each subject cohort (AML or DLBCL). This results in a study sample size of up to approximately 56 subjects. There will be a maximum of 14 patients in each of the pre-specified dose levels for DLT evaluation. All AML subjects participating in the 20 mg BID regimen of the MK-8628-001 protocol (approximately up to 3 subjects) will count toward the initial 6 AML subjects needed for the 20 mg BID dose level in this study. The sample size (in AML 20mg BID cohort) of PN005 will be reduced according to the number of AML 20mg BID patients treated in PN001. PN005 will be analyzed on its' own but relevant results (limited to the AML 20mg BID cohort) in PN001 will be described in the clinical study report of PN005. And the DLT information for the AML 20mg BID cohort in PN001 will be used together with the AML 20mg BID cohort in PN005 for dose escalation/de-escalation decisions and RP2D decisions. The final sample size will depend on the number of patients experiencing DLTs at each dose level, and may be increased if additional dose levels are required. For ORR, the sample size will be dependent on the number of subjects in each cohort. [Table 11](#) below provides Bayes credible interval and confidence interval with different number of events or responses for sample sizes of 6 and 14 to characterize the precision of the estimates for DLT rate and ORR, respectively.

Table 11 Bayes credible interval for DLT rate estimate and confidence interval for ORR estimate for different sample sizes and number of events

Sample Size	Number of Events or Responses	Observed Rate	80% Bayes credible interval	95% Bayes credible interval	95% confidence interval a
6	0	0	(0, 0.205)	(0, 0.348)	(0, 0.459)
6	1	0.167	(0.040, 0.391)	(0.013, 0.527)	(0.004, 0.641)
6	2	0.333	(0.146, 0.567)	(0.081, 0.685)	(0.043, 0.777)
6	3	0.500	(0.279, 0.721)	(0.184, 0.816)	(0.118, 0.882)
14	0	0	(0, 0.102)	(0, 0.181)	(0, 0.232)
14	1	0.071	(0.014, 0.194)	(0.004, 0.281)	(0.002, 0.339)
14	2	0.143	(0.053, 0.283)	(0.027, 0.373)	(0.018, 0.428)
14	3	0.214	(0.102, 0.367)	(0.062, 0.456)	(0.047, 0.508)
14	4	0.286	(0.156, 0.445)	(0.105, 0.533)	(0.084, 0.581)
14	5	0.357	(0.215, 0.519)	(0.154, 0.605)	(0.128, 0.649)

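### A routine scan used as the DLBCL baseline may be up to 42 days old at first dose and may predate the end of prior therapy, so change not due to MK-8628 can enter ORR, DCR and PFS

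*Combined protocol and SAP*

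**What the plan says.** Three places in the protocol let imaging from routine care serve as the DLBCL screening assessment if it is at most 4 weeks old at study entry: section 7.1.2.7.2, footnote g of the flow chart (section 6.0), and section 7.1.5.1. In the words of section 7.1.2.7.2, such imaging "performed outside of the scope of this study will be acceptable to complete the criteria for response assessment at screening".

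- **Anchor date.** Section 5.1.2: "Study entry is defined as the date that subject provides written informed consent".
- **Consent to first dose.** Section 1.0: "After a screening phase of up to 2 weeks, eligible subjects will receive treatment". The flow chart places consent in the Day -14 to -1 column.
- **No cap from the 2-week screening rule.** Section 7.1.5.1 lists this imaging as an exception to that rule: "The following is applicable to DLBCL subjects only: routine imaging (or bone marrow biopsy) performed outside of the scope of this study will be acceptable".
- **Washout.** Inclusion criterion 4 asks for at least 3 weeks since chemotherapy and most other anticancer therapy. It asks for 6 weeks for nitrosoureas or mitomycin C, and has half-life rules for antibodies and other non-cytotoxic agents. It does not say to which date the interval runs. Section 5.5.1 allows "Chemotherapy, hormone therapy or any other anticancer therapy or surgical intervention resection performed" at least 3 weeks before study start, a term not defined for the individual subject.
- **Renewing the baseline.** Section 7.1.2.8.2 prefers a new scan when a target lesion was biopsied during eligibility assessment. Nothing addresses therapy given between the scan and first dose.

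The first scheduled on-treatment scan is at Week 12. The statistical section (8.0) has no rule or sensitivity analysis for an old baseline.

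**The concern.** In Table 14 (section 12.5), partial response, stable disease and PET progression are judged by change from baseline. CT progression uses the nadir, which at Week 12 is the baseline unless an unscheduled scan was done. Whatever happens to the tumor between the baseline scan and first dose is therefore counted as if it happened on MK-8628.

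Two things can happen in that interval. If the scan precedes the end of the previous line, late shrinkage from that line makes MK-8628 look better. If the subject was untreated, growth makes it look worse. ORR and DCR are the secondary activity endpoints, PFS is exploratory, and early efficacy is one of the supporting inputs to the RP2D (section 5.2.1.4). The Lugano assessment also governs decisions tied to disease status, including discontinuation (section 7.1.2.7.2).

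The protocol dates other screening measures from first dose: blood count, coagulation and chemistry within 7 days, and the pregnancy test within 72 hours. The routine DLBCL scan is dated from consent.

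**Working it through.** **The plan's own figures.** Section 8.9 states: "There will be a maximum of 14 patients in each of the pre-specified dose levels for DLT evaluation". With two dose levels and two cohorts, 14 × 2 × 2 = 56, as stated. The Clopper-Pearson intervals in Table 11 reproduce to three decimals, for example 1/14 (0.002, 0.339) and 2/14 (0.018, 0.428). There is no power figure to check: "There are no statistical hypotheses for this study". The plan states no scan-to-first-dose interval, so that has to be derived.

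**Maximum age of a routine baseline scan.** Scan to consent ≤ 28 days; consent to first dose ≤ 14 days; total 28 + 14 = 42 days.

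**Overlap with prior therapy** (maximum scan age minus minimum washout):
- 3-week washout counted to first dose: 42 − 21 = 21 days.
- 3-week washout counted to consent: 28 − 21 = 7 days.
- 6-week washout: 42 − 42 = 0 days counted to first dose, and none counted to consent.
- Half-life rules: the overlap vanishes once the required interval reaches 42 days (first-dose reading) or 28 days (consent reading). For antibodies (3 half-lives) that is a half-life of 42/3 = 14 or 28/3 = 9.3 days. For other non-cytotoxic agents (5 half-lives) it is 42/5 = 8.4 or 28/5 = 5.6 days.

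For 3-week-washout therapy the overlap exists on either reading.

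**Share of the first assessment interval that precedes MK-8628.** Week 12 is day 84. With a 42-day-old scan, 42/(42 + 84) = 42/126 = 33%. At 28 days, 28/112 = 25%. At 14 days, the limit for a protocol screening scan, 14/98 = 14%.

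**Illustration of untreated growth.** The documents give no growth rate, so these are assumptions. With exponential growth, volume doubling time Td and lesion area (PPD) proportional to volume^(2/3), area grows by 2^((2/3) × gap/Td). The last row takes Td as the doubling time of area itself, 2^(gap/Td).

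| Gap to first dose | Td 30 d | Td 60 d | Td 120 d | Td at which area is up 50% |
|---|---|---|---|---|
| 14 d (volume) | ×1.24 | ×1.11 | ×1.06 | 16 d |
| 28 d (volume) | ×1.54 | ×1.24 | ×1.11 | 32 d |
| 42 d (volume) | ×1.91 | ×1.38 | ×1.18 | 48 d |
| 42 d (area) | ×2.64 | ×1.62 | ×1.27 | 72 d |

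A 50% rise in PPD is only one of the conditions for CT progression. Table 14 also requires a minimum diameter and an absolute increase. Growth also raises the bar for response: with volume Td of 60 days and a 42-day gap, a recorded 50% fall in SPD needs a true fall from first dose of 1 − 0.5/1.38 = 64%, against 1 − 0.5/1.11 = 55% with a 14-day gap.

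**Effect of one misclassified subject on ORR.** 1/28 = 3.6 points for the full DLBCL cohort, 1/14 = 7.1 for a full dose level, 1/6 = 16.7 for a minimum dose level. For scale, MK-8628-001 had 4 responses in 48 lymphoma subjects (8.3%; section 4.1.1.3), but those were all lymphomas, not only DLBCL.

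**The case against.** Several counter-arguments carry weight.

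- **Who is affected.** The default is a screening PET/CT within 14 days of first dose. Only subjects with a substituted routine scan are exposed, and the documents do not say how many that is. This stands.
- **Existing protection.** Section 5.1.2 requires a non-irradiated mass, which limits carry-over from radiotherapy. Section 8.4.2 counts only confirmed CR or PR, and scheduled scans are 12 weeks apart. Complete metabolic response is scored against mediastinal and liver uptake, not as change from baseline. Imaging is also required on clinical suspicion of progression. So a reader who infers that earlier shrinkage is simply credited as response goes too far. These protections are partial: a confirming scan uses the same old baseline, and stable disease in DCR needs no confirmation.
- **A tempting example.** Chemotherapy ending on Day -21, consent on Day -14 and a scan on Day -42 might be read as compliant throughout. It is compliant only if washout runs to first dose; counted to consent, that subject is ineligible. The DLBCL blood count thresholds, with 4 weeks free of transfusion for platelets and hemoglobin, narrow the group further.
- **Growth figures.** A reader might infer that many subjects would meet the 50% threshold before treatment. That rests wholly on an assumed doubling time, and the cut-off moves from 72 to 48 days with the choice of area or volume.
- **Consequence.** DLT rate drives the RP2D and efficacy is supportive. One subject's reclassification is small beside intervals as wide as those in Table 11.
- **Timing.** Enrollment is closed, so new screening wording alters no existing scan. This stands and shapes the remedy.

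**Conclusion.** The point holds as a weakness in how a routine DLBCL baseline is dated. The rules allow a scan up to 42 days before first dose, and for 3-week-washout therapy up to 21 or 7 days before the end of that therapy, depending on the washout reference date. No provision requires otherwise. The 42 days assume consent at the start of the 14-day screening window.

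A reader might infer that ORR is biased upward, or that the dose recommendation is compromised. The documents support neither: carry-over and untreated growth pull in opposite directions, and the share of routine scans, the growth rates and hence the net effect are unknown. The supported conclusion is that such change can be attributed to MK-8628, with each misclassified subject worth 3.6 to 16.7 ORR points depending on the denominator. Efficacy is analyzed in all treated subjects, so replacements could take the cohort denominator slightly above 28. The primary DLT endpoint is untouched. The change is worth making, but the trial's main conclusion does not depend on it.

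**What to change.** **Wording.** In sections 7.1.2.7.2 and 7.1.5.1 and flow-chart footnote g, accept routine imaging as baseline only if it was done within 28 days before the first dose of MK-8628 and after the last dose of any prior anticancer therapy. Otherwise use the screening PET/CT that the flow chart already schedules. Both conditions are needed: 28 days alone leaves 28 − 21 = 7 days of overlap when washout is counted to first dose. This lessens carry-over but does not remove it, since a scan on the day after the last chemotherapy dose would still pass. With enrollment closed, the wording matters mainly if the text is reused.

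**Analysis.** For each DLBCL subject, list the dates of baseline scan, last prior therapy and first dose. Repeat ORR, DCR and PFS without subjects whose baseline fails either condition, beside the all-treated analysis. Section 8.0 provides for a supplemental SAP before final database lock; after lock, label the analysis post hoc in the study report. Section 10.7 intends publication even after early termination, so the check still has a use.

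**Reconcile.** Sections 5.1.2 and 5.5.1 should give one reference date for the washout; the protocol's authors must choose it.

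**Cost.** Three wording edits, one listing and one sensitivity analysis. Under the new wording some subjects could no longer substitute an older routine scan and would have the scheduled screening scan.
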